Similarly, the accumulation ratio, RCmax will be estimated, using Cmax calculated on Day 14 and on Day 1. The analysis will be analogous to that described above for the estimation of Ro, replacing AUC by Cmax.

Time Invariance

The time invariance ratio will be calculated as the ratio of AUC(0- τ) on Day 14 over AUC(0-inf) on Day 1. The time invariance ratio will be listed and summarized along with other PK parameters. An analysis of variance (ANOVA) with subject as a random effect and day as a fixed, categorical effect will be conducted by dose on the log-transformed AUC. The time invariance of GSK3036656 will be assessed by calculating the ratio of the generalized least square means of AUC(0- τ) on Day 14 to AUC(0-inf) on Day 1, along with the corresponding 90% CI at each dose level. AUC(0-inf) on Day 1 will be the reference phase in the analysis, while AUC(0- τ) on Day 14 will be the test phase.

Achievement of Steady State (Repeat Dose Study Phase)

Trough concentration levels, C_τ , collected pre-morning dose will be plotted by collection day and dose.

To evaluate whether steady state was achieved, statistical analysis of C_τ will be performed after a log-transformation of the dose data. A mixed effect model will be fitted with dose, day and dose-by-day interaction as fixed effects (with dose as a factor and day as a continuous covariate) and subject as a random effect. The coefficients of the slopes for the day effect for each dose, along with corresponding 90% confidence intervals, will be used to determine whether steady state was achieved. If the day-by-dose interaction were not significant, then the point estimates and 95% CIs for the individual dose levels will also be pooled across all doses for a single D14/D1 ratio.

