
 Point estimates and 90% confidence intervals for the differences “Day 14- Day 1” will be constructed using the appropriate error term. The point estimates and associated 90% confidence intervals will then be exponentially back-transformed to provide point and 90% confidence interval estimates for the ratios “Day 14: Day 1” for each active dose. If both the dose and day by dose interaction terms are not significant, a single point estimate and confidence interval pooled across all doses will also be constructed.
--

Pharmacokinetic Statistical Analyses (Achievement of Steady State - Repeat Dose Study Phase)

Endpoint(s)

• Trough plasma concentrations at the end of the dosing interval (C _T)
--

Model Specification

 Will be statistically analysed using a mixed models (MM) using log-transformed dose data. Fixed effects : dose, day and dose*day Random Effect : Subject

 The Kenward and Roger method for approximating the denominator degrees of freedom and correcting for bias in the estimated variance-covariance of the fixed

Pharmacokinetic Statistical Analyses (Achievement of Steady State - Repeat Dose Study Phase)

effects will be used.

- An unstructured covariance structure for the G matrix will be used.
 - In the event that this model fails to converge, alternative covariance structures may be considered such as VC or CS.
 - Akaike's Information Criteria (AIC) will be used to assist with the selection of covariance structure.

Model Checking & Diagnostics

- Refer to [Appendix 8: Model Checking and Diagnostics for Statistical Analyses](#).

Model Results Presentation

The coefficients of the slopes for the day effect for each dose, along with corresponding 90% confidence intervals, will be used to determine whether steady state was achieved. If the day-by-dose interaction were not significant, then the point estimates and 95% CIs for the individual dose levels will also be pooled across all doses for a single D14/D1 ratio.

Trough concentration levels collected pre-morning dose will be plotted by collection day and dose.

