Cmax (µg/mL)	XXmg	Fed vs Fasted	xx	x.xxx	xx	x.xxx	x.xxx	(x.xxx, x.xxx)
T1/2 (µg/mL)	XXmg	Fed vs Fasted	xx	x.xxx	xx	x.xxx	x.xxx	(x.xxx, x.xxx)

Example : PK_T3
Protocol : GSK3036656
Population : Pharmacokinetic

Page 7 of n

Table PK_T3
Non-Parametric Analysis of Pharmacokinetic Parameter Assessing Food Effect -Tmax Part A

Parameter (units)	Treatment	Comparison	Median				Diff	90% Confidence Interval
			n	Test	n	Ref		
Tmax (μg/mL)	XXmg	Fed vs Fasted	xx	x.xxx	xx	x.xxx	x.xxx	(x.xxx, x.xxx)

Example : PK_T4
Protocol : GSK3036656
Population : Pharmacokinetic

Page 8 of n

Table PK_T4
Statistical Analysis of log transformed plasma GSK3036656 Pharmacokinetic Parameters Assessing Time Invariance Part B

Parameter (units)	Treatment	Comparison	Ratio	90% Confidence Interval
AUC (0- τ) ($\mu\text{g.h/mL}$) Vs AUC (0-inf) ($\mu\text{g.h/mL}$)	XXmg	Day 14 vs Day	x.xxx	(x.xxx, x.xxx)

Example : PK_T5
Protocol : GSK3036656
Population : Pharmacokinetic

Page 9 of n

Table PK_T5
Statistical Analysis of log transformed plasma GSK3036656 Pharmacokinetic Parameters Assessing Accumulation Ratio Part B

Parameter (units)	Treatment	Comparison	Geom.LsMean		Ratio		90% Confidence Interval
			n	Test	n	Ref	
AUC (Ro) (µg.h/mL)	XXmg	Day 14 vs Day 1	XX	x.xxx	xx	x.xxx	x.xxx (x.xxx, x.xxx)
Cmax (RCmax) (µg/mL)	XXmg	Day 14 vs Day 1	XX	x.xxx	xx	x.xxx	x.xxx (x.xxx, x.xxx)

Example : PK_T6
Protocol : GSK3036656
Population : Pharmacokinetic

Page 10 of n

Table PK_T6
Statistical Analysis of log transformed plasma GSK3036656 Pharmacokinetic Parameters Assessing Steady State Part B

Parameter	Treatment	Day	Back-Transformed Slope	90% Confidence Interval
Ctrough	xxmg	1-14	x.xxxx	(x.xxxx, x.xxxx)

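### The steady-state analysis gives per-dose trough slopes 90% intervals, then pools undefined 95% intervals into a D14/D1 ratio that its day-slope model does not estimate

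*SAP*

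**What the plan says.** SAP 7.2.1.3.2, Achievement of Steady State, fits a mixed model to troughs with dose, day and their interaction as fixed effects and subject as a random effect. Protocol 10.3.2.2 adds that day is a continuous covariate, so the model yields a slope per day.

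- **Per dose.** The day slopes "for each dose, along with corresponding 90% confidence intervals, will be used to determine whether steady state was achieved".
- **Pooled.** The next sentence begins "If the day-by-dose interaction were not significant, then the point estimates and 95% CIs for the individual dose levels will also be pooled across all"; the result it names is one D14/D1 ratio.
- **Protocol.** Section 10.3.2.2 has the same pair of statements, the second reading "then the point estimates and 95% CIs for the individual dose levels will also be pooled across all doses for a single D14/D1 ratio". The SAP inherited the mismatch, and neither document settles the other. SAP 2.1 lists only the Bayesian random effect as a change from the protocol.
- **Shell PK_T6 (SAP 10.11).** It has a "Back-Transformed Slope" column with a 90% interval, one line per dose, a day label of 1-14, and no pooled line.
- **Neighbouring analyses.** Accumulation uses 90%: "The point estimates and associated 90% confidence intervals will then be exponentially back-transformed". Its pooling statement asks for one estimate and one interval across doses and names no other level. Dose proportionality, food effect and time invariance also use 90%. In that section 95% otherwise appears only for descriptive means.

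**The concern.** Two things are wrong as written.

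**The level.** The pooling sentence relies on 95% intervals by dose that the analysis never produces. An analyst must either compute a second set of slope intervals or treat 95% as a slip for 90%. If the interval is used to judge whether troughs have levelled off, the wider one is the more lenient, because it more easily includes zero slope.

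**The quantity.** The per-dose output is a slope per day and the pooled output is called a D14/D1 ratio. No conversion is given. A ratio of Day 14 to Day 1 troughs exceeds 1 through accumulation even when steady state has been reached, so it cannot answer the steady-state question at either confidence level. The sentence also speaks of pooling the intervals themselves, rather than estimating one pooled effect with its own interval.

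What is at stake is the reporting of a secondary objective (achievement of steady state, as data permit). No formal hypothesis is tested, so no error rate is affected.

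**Working it through.** The plan gives no figure to reproduce here: Protocol 10.2 used no sample-size calculation, and no pass rule is stated.

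**Inputs from the documents**
- 8 active subjects per cohort, up to 4 cohorts: N = 32 (Protocol 4.2).
- Troughs pre-dose on Days 12, 13 and 14 and 24 h after the Day 14 dose, i.e. Days 12 to 15 (Protocol 7.3.1).
- Predicted half-life about 30 h, range 12 to 72 h (Protocol 4.1).

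**Assumptions**
- Linear one-compartment PK with once-daily dosing.
- Log trough as the response. The text speaks of log-transforming dose data, but PK_T6 back-transforms the slope.
- Within-subject log-SD of 0.10 to 0.20.
- An interval that includes zero slope is read as steady state.

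**1. Same estimate, two levels.** Normal quantiles: 1.960/1.645 = 1.19. With t on 32×4 − 32 − 1 = 95 df: 1.985/1.661 = 1.20.

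**2. How often the level changes the pooled reading.** After n doses the log trough is log(1 − exp(−24nk)) plus a constant, with k = ln2/half-life. The least-squares slope over n = 11 to 14 is 0.0006 per day at 30 h and 0.0139 at 72 h. For four consecutive days the sum of squares is 5, so SE = SD/√(5×32). At SD 0.10 this is 0.10/√160 = 0.0079, and the expected t at 72 h is 0.0139/0.0079 = 1.76. The non-central t distribution gives:

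| Half-life | SD | 90% interval includes 0 | 95% interval includes 0 | Difference |
|---|---|---|---|---|
| 72 h | 0.10 | 0.458 | 0.586 | 0.13 |
| 72 h | 0.15 | 0.682 | 0.787 | 0.10 |
| 72 h | 0.20 | 0.774 | 0.859 | 0.09 |
| 30 h | 0.10–0.20 | 0.90 | 0.95 | 0.05 |

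**3. Pooled 95% against per-dose 90%.** With K equal, independent doses, the half-width ratio is (1.960/1.645)/√K: 0.84, 0.69 and 0.60 for K = 2, 3 and 4. The pooled interval is the narrower one. If every dose has z = 1.645, the pooled z is 1.645√K = 2.33, 2.85 and 3.29, all beyond 1.960.

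**4. Source of per-dose/pooled disagreement.** By simulation with K = 4 and no true slope, at least one dose excludes zero at 90% while the pooled interval includes it in 30.1% of cases (pooled at 95%) and 26.7% (pooled at 90%). The level accounts for 30.1 − 26.7 = 3.4 points. Over K = 2 to 4 and a true per-dose z of 0 to 1.5, it accounts for 3.0 to 8.4 points.

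**5. What a D14/D1 trough ratio measures.** The trough 24 h after dose 14 over that 24 h after dose 1 is (1 − exp(−14×24k))/(1 − exp(−24k)): 1.33 at 12 h, 2.35 at 30 h and 4.66 at 72 h. Extrapolating the Day 12–15 slope at 30 h over 13 days gives exp(13×0.0006) = 1.01 instead of 2.35. The two readings of the ratio are therefore not interchangeable.

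**6. Literal pooling of limits.** Averaging four per-dose 95% intervals at SD 0.10 gives a half-width of 1.985×0.10/√40 = 0.0314. A model-based pooled 90% interval gives 1.661×0.10/√160 = 0.0131. The factor of 2.4 is 1.2 from the level times 2 from not gaining precision.

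**7. The day range.** PK_T6 says 1-14. Adding troughs 24, 48 and 72 h after Day 1 (n = 1, 2, 3) raises the sum of squares to 196. At 30 h the slope becomes 0.048, and at SD 0.10 t = 0.048/(0.10/√(196×32)) = 38; at SD 0.20 it is 19. At 12 h, t is 5 to 10. Both levels then exclude zero.

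**The case against.** The strongest reply is that this is an editorial slip in a supplementary output. The determining statement concerns per-dose slopes at 90%. The pooled result is conditional and additional, and nothing says that it decides steady state. The study is estimation-only, and dose escalation rests on safety, tolerability and exposure (Protocol 6.3), not on this interval. All of that stands and keeps the point minor.

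A reader might infer that the mismatch lets a borderline slope fail at each dose and then pass when pooled. The documents do not support that as a consequence of the level. A properly pooled 95% interval is narrower than a per-dose 90% one, so a borderline slope shared by all doses also excludes zero when pooled. Most disagreement comes from averaging a steeper dose with flatter ones, and it would remain with 90% throughout.

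A reader might also infer that 95% relaxes a steady-state criterion. No criterion is written, and reading inclusion of zero as steady state is an assumption made here.

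The size is also conditional. The 9 to 13% belongs to the 72 h extreme of the predicted range. If early troughs enter, as the PK_T6 label suggests, the level makes no difference at 12 or 30 h. The factor of 2.4 needs someone to average interval limits literally.

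None of this explains a 95% interval that the analysis does not define, or a ratio that its model does not deliver.

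**Conclusion.** The inconsistency is certain and appears in both documents: 90% per-dose slopes, then pooled 95% intervals with no definition, labelled as a ratio that would reflect accumulation. PK_T6 and the other modelled PK analyses point to 90% as the intended level.

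The effect is small. On the same pooled slope the level alone changes the reading in about 5% of trials at 30 h and 9 to 13% at 72 h. This assumes troughs from Days 12 to 15, 32 active subjects, within-subject log-SD 0.10 to 0.20 and the unwritten includes-zero rule. The mislabelled ratio matters more for interpretation: about 2.35 at a 30 h half-life with steady state effectively reached. Severity is minor.

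**What to change.** In SAP 7.2.1.3.2, Achievement of Steady State, replace the pooling sentence with: *If the day-by-dose interaction is not significant, a single pooled day slope and its 90% CI, estimated from the model without the interaction, will also be reported.* Then:

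- State that this replaces the D14/D1 ratio. This changes the quantity as well as the level; accumulation is already estimated separately through Ro and RCmax.
- Say whether the pooled slope informs the steady-state conclusion and, if so, how its interval is read.
- Add a pooled line to PK_T6 and make its day range match the trough days analysed.
- Record the departure from Protocol 10.3.2.2 in SAP 2.1, and align the protocol text if it is amended.

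The cost is one sentence, one table line and one change-log entry, with no new data. The one downside is that, at 90% instead of 95%, the pooled slope is slightly less likely to be read as steady state.

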
repeat oral doses, as data permit
 
 • To examine the extent of accumulation and achievement of steady-state following repeat oral doses of GSK3036656, as data permit • To define the metabolic profile of GSK3036656 by identifying and quantifying, where possible and appropriate, GSK3036656-related material in plasma and urine following a single and repeated oral administration of GSK3036656 	
of dose proportionality
 
 • Observed accumulation ratio based on AUC(Ro) and Cmax (RCmax) and steady-state ratio (Rss) following repeat dosing • Trough plasma concentrations at the end of the dosing interval (C_T) to assess the achievement of steady-state of GSK3036656 following repeat oral doses • Structure and concentration of GSK3036656-related material in plasma and urine

Overall Design

Treatment Arms and Duration

Part A:

For the single dose part, there will be up to 2 cohorts with up to 4 treatment (dosing) periods in each cohort (including a food effect treatment period). Initially, there will be a 14 day wash out period for individual subjects between each dose level which is considered sufficient in light of the predicted half-life of GSK3036656 [on average, approximately 30 hours (range: 12 to 72 hours) based on the various preclinical extrapolation methods], however this may be revised once relevant PK data is obtained. 9 subjects per cohort will be enrolled and randomised to ensure adequate safety, tolerability and PK information is gained and a balanced randomisation is achieved across all treatment (dosing) periods.

During each treatment (dosing) period, GSK3036656 will be administered to 6 subjects and placebo will be administered to 3 subjects. As this is a FTIH study, each treatment (dosing) period will be staggered over 2 days. On Day 1, one subject will receive GSK3036656 and one subject will receive placebo. The remaining subjects will be dosed one day later provided satisfactory safety and tolerability is demonstrated for the subjects dosed on Day 1. A treatment (dosing) period does not have to be staggered if the dose administered is equal to or lower than a dose that has been already tested and found to be safe and well tolerated.

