7.3. Pharmacokinetics

7.3.1. Blood Sample Collection

Blood samples for plasma PK analysis of GSK3036656 will be collected into K3 EDTA tubes at the time points indicated in the Time and Events Table (Section [7.1](#)). The actual date and time of each blood sample collection will be recorded. In the repeat dose part of the study on days 12 and 13, PK samples will be taken pre-dose to assess the achievement of steady-state of GSK3036656 following repeat oral doses. On the last dosing day of the repeat dose, subjects will undergo the same assessments as on Day 1. Subjects may then be discharged but will be required to return for the 36, 48 and 72 hour PK sampling. PK samples obtained on pre-dose and 24 hours post-dose on day 14 will also be used as part of the assessment to see if steady-state has been achieved.

The timing of PK samples may be altered and/or PK samples may be obtained at additional time points to ensure thorough PK monitoring.

Details of PK blood sample collection (including volume to be collected), processing, storage and shipping procedures are provided in the SRM.

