7.2.1.3. Pharmacokinetic Parameters

7.2.1.3.1. Deriving Pharmacokinetic Parameters

- Refer to [Appendix 4](#): Data Display Standards & Handling Conventions (Section 10.4.3. Reporting Process & Standards).
- Plasma GSK3036656 concentration-time data will be analyzed by non-compartmental methods according to current working practices with WinNonlin 5.2 or higher.
- Non-compartmental analysis will be performed in accordance with GSK PK Guidance document GUI_51487.
- All calculations of non-compartmental parameters will be based on actual sampling times recorded during the study.
- Pharmacokinetic parameters described in [Table 5](#) will be determined from plasma concentration-time data and urine concentration data, as data permits.

Table 5 Derived Pharmacokinetic Parameters

Parameter	Parameter Description
AUC(0-t)	Area under the concentration-time curve from time zero to the time of the last quantifiable concentration (C(t)) will be calculated using the linear trapezoidal rule for each incremental trapezoid and the log trapezoidal rule for each decremental trapezoid.
AUC(0-∞)	Area under the concentration-time curve extrapolated to infinity calculated as: $\text{AUC} = \text{AUC}(0-t) + C(t) / \lambda_z$
AUC(0-24h)	Area under the concentration-time curve from time zero to 24 hours post-dose
AUC(0-τ)	AUC from time zero during a dosing interval of duration “τ”
AUC(Ro)	Observed accumulation ratio (Ro) for AUC will be calculated as follows: $\text{Day 14 AUC}(0-\tau) / \text{Day 1 AUC}(0-\tau)$
Ae	Urinary excretion of unchanged drug
Cmax	Maximum observed blood concentration, determined directly from the concentration-time data.

Parameter	Parameter Description
Ctrough	Pre-dose observed concentration, will be obtained directly from the concentration-time data.
CLr	Renal clearance
Fe	Fraction of the dose excreted in the urine
Lambda_z	The first order rate constant associated with the terminal (log-linear) portion of the concentration-time curve.
Rss	Steady state ratio (Rss) will be calculated as follows: Day 14 AUC(0- τ)/Day 1 AUC(0- ∞)
RCmax	Observed accumulation ratio for Cmax (RCmax) will be calculated as follows: Day 14 Cmax/Day 1 Cmax
tmax	Time to reach Cmax, determined directly from the concentration-time data.
t _{1/2}	Apparent terminal phase half-life will be calculated as: $t_{1/2} = \ln 2 / \text{Lambda}_z$ (NOTE: Lambda_z is the terminal phase rate constant).

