2.15.	PK	Non-Standard PK_T6	Statistical Analysis of log transformed plasma GSK3036656 Pharmacokinetic Parameters Assessing Steady State– Part B	Only for Repeat Dose Study Phase	SAC

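### The steady-state analysis does not settle which troughs it uses; the table shell and the pooled Day 14/Day 1 ratio point to a measure of accumulation, not of a plateau

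*SAP*

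**What the plan says.** Achievement of steady state is a secondary objective in both documents. The places that bear on it are these.

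- **Protocol 7.3.1** assigns samples to the assessment: "on days 12 and 13, PK samples will be taken pre-dose to assess the achievement of steady-state", and "PK samples obtained on pre-dose and 24 hours post-dose on day 14 will also be used as part of the assessment".
- **Protocol 10.3.2.2 and SAP 7.2.1.3.2 (Achievement of Steady State)** fit dose, day, dose-by-day and a random subject effect. The protocol makes day continuous. Per-dose day slopes with 90% CIs are to determine whether steady state was reached. The model text names no days and gives no decision rule.
- **The same two sections** add, if the interaction is not significant, that "the point estimates and 95% CIs for the individual dose levels will also be pooled across all doses for a single D14/D1 ratio".
- **SAP Appendix 11, shell PK_T6**, reports a "Back-Transformed Slope" for Ctrough over Days 1–14.
- **SAP Table 5** defines Ctrough as "Pre-dose observed concentration, will be obtained directly from the concentration-time data". The steady-state endpoint in SAP 7.2.1.3.2 is instead the concentration at the end of the dosing interval.
- **Protocol 10.3.2.2** says the analysis "will be performed after a log-transformation of the dose data", and the SAP repeats this. SAP Table 2.15 is titled "Statistical Analysis of log transformed plasma GSK3036656 Pharmacokinetic Parameters Assessing Steady State", so log trough is evidently meant.

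The accumulation analysis just before it pools the Day 14:Day 1 ratio across doses only if both the dose and the dose-by-day terms are non-significant.

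**The concern.** A slope test for steady state makes sense only over days on which a plateau could already exist. Protocol 7.3.1 supplies such a window; the shell and the pooled ratio do not. If the 24, 48 and 72 h samples of the Day 1 profile are taken as Day 2–4 troughs, one straight line covers both the build-up and the plateau. Its slope is then positive even when the plateau is complete.

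The ratio has a further problem. With the Table 5 definition, the Day 1 trough precedes any drug, so its log is undefined. With the end-of-interval definition, the ratio measures accumulation, which Ro and RCmax already estimate in their own analysis.

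An analyst could therefore follow the plan and reach opposite conclusions from the same data. In the accumulation section, the extra condition on the dose main effect can block the pooled ratio for an irrelevant reason: on un-normalised AUC or Cmax, a dose effect only says that higher doses give higher exposure.

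**Working it through.** The plan states no error rate or precision for this analysis, so there is no figure to reproduce.

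**Inputs.** Half-life 30 h, range 12–72 h (protocol synopsis); once-daily dosing for 14 days and 8 active subjects per cohort (protocol 4.2). Assumed: one compartment with instantaneous input, and residual CV of 15, 25 or 40%.

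**Trough after n doses**, with q = 2^(−24/t½), is proportional to q(1 − qⁿ)/(1 − q). As a fraction of steady state it is 1 − qⁿ. The pre-dose trough on Day d follows d − 1 doses; the sample 24 h after the Day 14 dose is called Day 15. At 30 h, q = 0.574. The Day 2, 3 and 4 troughs are 43%, 67% and 81% of plateau, and Day 12 is 1 − 0.574¹¹ = 99.8%.

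**Back-transformed least-squares slope of log trough per day, and the end-of-interval Day 14/Day 1 ratio (1 − q¹⁴)/(1 − q):**

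| t½ | Day 12 trough, % of plateau | Days 2–4, 12–14 | Days 2–4, 12–15 | Days 12–15 | Day 14/Day 1 |
|---|---|---|---|---|---|
| 12 h | 100 | 1.014 | 1.013 | 1.0000 | 1.33 |
| 30 h | 99.8 | 1.053 | 1.049 | 1.0006 | 2.35 |
| 72 h | 92.1 | 1.111 | 1.105 | 1.014 | 4.66 |

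The ratio does not approach 1 at a plateau. If it were instead read off the fitted Day 2–4, 12–14 line, it would be exp(13 × 0.0516) = 1.96 at 30 h, against a true 2.35. It would then not be a correct accumulation ratio either.

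**How often the 90% CI of the slope excludes 1** (20,000 simulated cohorts of 8, random-intercept model, CV 15 / 25 / 40%):

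| t½ | Days 2–4, 12–14 | Days 12–15 |
|---|---|---|
| 12 h | 90% / 57% / 33% | about 10% |
| 30 h | 99.7–100% | about 10% |
| 72 h | 100% | 11–16% |

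Adding Day 15 to the long window raises the 12 h rates by only a few points. A two-sided 90% interval excludes a true value of 1 in 10% of trials, so the late window behaves as it should at 12 and 30 h.

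**Accumulation pooling.** Assume dose-proportional exposure, 50% between-subject CV (variance ln 1.25 = 0.223), 8 per cohort, alpha 0.05 and 1.5-fold dose steps. The non-centrality is 8 × Σ(log dose − mean)²/0.223:

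- two cohorts: 8 × 0.082/0.223 = 2.9, dose term significant in 36% of trials
- three cohorts: 8 × 0.329/0.223 = 11.8, significant in 82%
- four cohorts: 8 × 0.822/0.223 = 29.5, significant in 99%

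With doses at 1:1.25:1.5:1.75 the rate is 48%. At within-subject CV 25% (s = 0.246) and four cohorts, the 90% CI factor is exp(1.701 × 0.246 × √(2/8)) = 1.23 per dose and exp(1.701 × 0.246 × √(2/32)) = 1.11 pooled.

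**The case against.** The best defence is that the days are in fact specified. Protocol 10.3.2.2 says that troughs from specified days serve the steady-state assessment, and only protocol 7.3.1 assigns any. A Day 12–15 slope fits the SAP model text. The Day 1–14 entry sits in an example shell whose neighbours contain evident slips, such as Tmax in µg/mL. No text assigns the Day 2–4 samples to this model, so the rates near 100% depend on that reading. The ratio is only an additional pooled output, while the per-dose slopes decide. The objective is secondary, troughs will be plotted by day, and the error runs mainly towards declaring steady state not reached.

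Much of this is fair. It limits the consequence and shows which window was probably intended. It does not remove the conflict: the shell and the ratio are the SAP's only indications of a day range for this analysis, and both disagree with protocol 7.3.1. It is also true that the late window has low power at long half-lives, and that the remedy below supplies no pass/fail rule. The accumulation point costs only a supplementary pooled estimate, since per-dose ratios are reported in any case.

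**Conclusion.** The concern holds. The documents give irreconcilable indications of which troughs enter the analysis. At a 30 h half-life the two readings would lead almost always to different conclusions: the CI excludes 1 in 99.7–100% of cohorts against about 10%, although the trough is within 0.2% of plateau from Day 12. At 12 h the contrast is 33–90% against about 10%. The Day 14/Day 1 ratio (1.33–4.66 over the predicted half-life range) is the wrong quantity for steady state under either trough definition.

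The exact rates rest on a one-compartment model, assumed CVs, and the Day 1-profile samples being used as Day 2–4 troughs. The direction does not depend on the CVs: any straight line through build-up and plateau slopes upward. The reference to log-transformed dose is a drafting slip and plays no part in this bias. The change from 90% to 95% CIs on pooling is a separate inconsistency.

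**What to change.** In SAP 7.2.1.3.2:

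- State that log_e(Cτ) is modelled from the four protocol 7.3.1 samples only: pre-dose Days 12, 13 and 14, and 24 h after the Day 14 dose. Day is continuous, dose is a factor, with dose-by-day and a random subject effect.
- Report exp(slope) with a 90% CI per dose, and pooled with a 90% CI if dose-by-day is non-significant.
- Delete the Day 14/Day 1 ratio, and replace the reference to log-transformed dose with log_e-transformed Cτ.
- Use one trough definition in Table 5 and in the endpoint. Change the day range in PK_T6 to 12–15. Show earlier troughs in the plot only.
- Add that a CI including 1 is read with the slope estimate and the trough plot, not as proof of steady state.
- In the accumulation section, make pooling depend on dose-by-day alone.

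The cost is SAP wording and one shell; every sample is already scheduled. The drawback is low power against slow residual accumulation. At 72 h the trough rises from 92% to 96% of plateau over Days 12–15 (1.014 per day), and the 90% CI excludes 1 in only 11–16% of trials per dose, or 13–33% pooled over four cohorts (n = 32), at CV 40–15%. The per-dose CI factor is 1.04–1.11 per day, which should be reported so that readers can see what was not ruled out.
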